5.4. Other Efficacy Variable(s)

5.4.1. Definition

Additional endpoints of interest include the following:

- Change from baseline in HbA_{1c} at Week 26 between canagliflozin 100 mg and placebo.
- Change from baseline in HbA_{1c} at Week 26 between canagliflozin 100 mg followed by a dose increase to 300 mg and placebo.
- Percent change from baseline in lipids at Week 26 and at Week 52 between canagliflozin and placebo.
- Change from baseline in SBP and DBP at Week 26 and at Week 52 between canagliflozin and placebo.

5.4.2. Analysis Methods

The comparisons by dose (canagliflozin 100 mg without up-titration after Week 12 and canagliflozin 100 mg up-titrate to 300 mg after Week 12) to placebo will be tested for reference purpose by using the weights in the analyses described below.

- When comparing the subjects who initially receive canagliflozin 100 mg with no dose increase to 300 mg to placebo: All subjects start with a weight of 1. After Week 12, subjects with an $HbA_{1c} \ge 7.0\%$ and eGFR $\ge 60 \text{ mL/min}/1.73\text{m}^2$ who are re-randomized to continue canagliflozin 100 mg will have a weight of 2. The subjects who are re-randomized to up-titrate to canagliflozin 300 mg will have a weight of 0.
- When comparing the subjects who initially receive canagliflozin 100 mg followed by a dose increase to 300 mg to placebo: All subjects start with a weight of 1. After Week 12, subjects with an HbA_{1c} ≥7.0% and eGFR ≥60 mL/min/1.73m² who are re-randomized to continue canagliflozin 100 mg will have a weight of 0 and those who are re-randomized to up-titrate to canagliflozin 300 mg will have a weight of 2.

Given that lipids are only collected at baseline, Week 26 and Week 52, the percent change in lipid parameters (except for triglycerides) will be analyzed using an analysis of covariance at Week 26 and at Week 52 with LOCF applied when the Week 26 or Week 52 values are missing. The model will be similar to the supportive approach listed in Section 5.2.3. The percent change in triglycerides will be analyzed using nonparametric methods as outlined below given its skewed nature. A Wilcoxon rank sum test will be performed to compare canagliflozin to placebo. Additionally, the Hodges-Lehman estimator for the difference in the medians and the distribution-free confidence intervals based on the Wilcoxon rank sum test (Hollander 2013) will also be provided.

The change from baseline in SBP and DBP will be analyzed using an MMRM model similar to the one used to analyze the primary efficacy endpoint.

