	efficacy analysis does not yield significant results. Analysis of the	
	primary efficacy endpoint based on copy reference multiple	
	imputation (MI) as well as tipping point analysis have been added	
	as sensitivity analyses. Additionally, supportive analyses have	
	been placed together for further clarity. Other minor editorial	
	changes have been made to provide clarity.	
Section 5.3 Secondary Efficacy Endpoints	Section updated to be consistent with Protocol Amendment 4	
References	The following reference has been deleted as it is no longer	
	applicable:	

Stenlöf K, Cefalu WT, Kim KA, et al. Efficacy and safety of
canagliflozin monotherapy in subjects with type 2 diabetes
mellitus inadequately controlled with diet and exercise. Diabetes
Obes Metab. 2013;15(4):372-382.

Amendment 3 (22 September 2023)

Applicable Section(s)	Description of Change		
The purpose of this amendment is to correct minor inconsistencies at few places in the description of the			
supportive analyses and subgroup analyses. Additionally, clarifying text is added to the description of the			
sensitivity analysis based on mixed model for repeated measures (MMRM).			
Section 5.2.3. Analysis Methods	Changes in the description of the sensitivity analysis based on		
	MMRM.		
	In the description of the sensitivity analysis of the primary efficacy endpoint based on mixed model for repeated measures (MMRM), the following sentence is added to consider other covariance structures in case the model does not converge using the unstructured covariance:		
	"In case the model does not converge using the unstructured covariance then alternative covariance structures (such as compound symmetry and AR (1)) will be considered."		
	Furthermore, since MMRM is not the primary efficacy analysis, the following sentence has been deleted:		
	"This sensitivity analysis will constitute the primary analysis based on a specific health authority request."		
	Changes in the description of re-randomization test		
	Since MMRM will be utilized to perform the re-randomization test, to be consistent, the phrase "primary efficacy comparison" have been replaced with "treatment comparison" as applicable at couple of places since primary efficacy comparison is based on Pattern Mixture Model (PMM) and not MMRM.		
	Changes in the description of subgroup analyses		

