1.5. Randomization and Blinding

Stratification

Dynamic randomization (ie, covariate-adjusted randomization) will be used to maintain balance between treatment groups with respect to the following stratification factors: AHA background (ie, diet and exercise only, metformin monotherapy, insulin monotherapy, or combination of metformin and insulin) and age group [≥ 10 to <15 years old, ≥ 15 to <18 years old]. The stratification process will be handled after logging on to the IWRS being used for the study.

Randomization

In dynamic randomization, a new subject is sequentially assigned to a particular treatment group by taking into account the specific covariates and previous assignments of subjects. This approach uses the method of minimization by assessing the imbalance of sample size among the covariates listed above. On Day 1, subjects will be randomized to 1 of 2 treatment groups based on a computer-generated dynamic randomization algorithm prepared by or under the supervision of the sponsor before the study. This approach seeks to maintain balance between treatment groups with respect to the AHA background and age group. The goal is to have at least 30% of randomized subjects that will be ≥ 10 to <15 years of age, 30% to 75% of participants will be female, and at least 20% in both age subsets (10 to <15 years, and ≥ 15 to <18 years) will be male, and 30% of participants that will have ethnicity and life-style comparable to Europe.

Re-randomization

At Week 12, subjects' glycemic status will be assessed by a central laboratory HbA_{1c} . Following the review of the Week 12 unmasked HbA_{1c} results and the Week 12 eGFR value, the following will occur:

- Subjects with HbA_{1c} value <7.0% or eGFR <60 mL/min/1.73 m2 will not be undergoing re-randomization and instead will be continuing their current treatment assignment (ie, canagliflozin 100 mg or matching placebo) for the remainder of the study.
- Subjects with HbA_{1c} value \geq 7.0% and eGFR \geq 60 mL/min/1.73 m2 will be re-randomized in a 1:1 ratio (in a blinded fashion via IWRS) to either.
 - remain on their original treatment assignment (ie, canagliflozin 100 mg or matching placebo) or
 - up-titrate canagliflozin 100 mg to 300 mg (or matching placebo). In order to keep the study blind, subjects randomized to the placebo group will undergo a mock up-titration.

Blinding

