5.2.3. Analysis Methods

Primary Analysis

The primary analysis is based on the FAS dataset, including all HbA1c measurements collected from randomization to Week 26, including the measurements collected after treatment discontinuation or initiation of rescue medication.

The primary analysis will be based on pattern mixture model (PMM), as described below:

- Any intermediate missing data will be multiply imputed using Monte Carlo Markov Chains (MCMC), under a Missing at Random (MAR) assumption.
- Then the participants with ICEs and missing Week 26 HbA1c values will be multiply imputed using a multiple imputation (MI) model based on the participants with ICEs and non-missing Week 26 HbA1c values. An MI regression will be applied to impute all monotone missing values, using treatment group, stratification factors, baseline HbA1c and the change from baseline in HbA1c at Weeks 6, 12 and 20. If this MI model does not converge then a Copy Reference MI model will be used instead, as described in the sensitivity analysis section.
- Any Week 26 missing values for change from baseline in HbA_{1c} in participants without ICEs will be imputed based on the MI regression (see description above) applied to all participants.
- A total of 1000 multiple imputations will be performed. A seed equal to 345 will be used in all MI models.
- After MI, each of the multiply imputed datasets will be analyzed using analysis of covariance (ANCOVA) with terms for treatment, stratification factors, and baseline HbA_{1c}.
- Rubin's rules will be applied to combine the ANCOVA results across the imputed datasets, including the Week 26 LS Means for each treatment group and the difference vs placebo in LS Means.

Secondary analysis of the primary efficacy endpoint

The secondary analysis is based on a subset of subjects on background metformin (with or without insulin) from the FAS dataset, including all HbA1c measurements collected from randomization to Week 26, including the measurements collected after treatment discontinuation or initiation of

rescue medication. The attributes of estimand for this analysis is the same as the primary efficacy estimand except the population is a subset of subjects with background metformin (with or without insulin). The same analysis based on PMM will be performed as described above.

Bayesian analysis of the primary efficacy endpoint

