5.3.2. Analysis Methods

The estimands for the secondary endpoints are the same as for the primary efficacy endpoint except for the variable.

Continuous endpoints (except for triglycerides) will be analyzed with an MMRM model as described before in the FAS population. For the endpoints with post-baseline assessments taken only at Week 26 and Week 52, an analysis of covariance (ANCOVA) model similar to the primary efficacy endpoint will be used at Week 26. The least-squares means for the treatment comparisons and their 2-sided 95% confidence intervals will be estimated based on this model. The analysis of percent change in triglycerides may be based on nonparametric methods (given the anticipated skewed nature of this parameter) or alternative methods.

The categorical secondary efficacy endpoint of maintaining HbA_{1c} <7.0% (and HbA_{1c} <6.5% and HbA_{1c} <7.5%) will be analyzed longitudinally using a generalized linear mixed model in the FAS population. The model will include the fixed, categorical effects of treatment, stratification factors (ie, background AHA and age group), visit, and treatment-by-visit interaction, as well as the fixed, continuous covariates of baseline and baseline-by-visit interaction. An unstructured covariance will be used to model the within-subject errors. The odds ratio and 2-sided 95% CI for the treatment comparisons at Week 26 (canagliflozin compared to placebo) will be estimated based on this model. It is possible that the generalized linear mixed model may fail to converge for the binary secondary efficacy endpoint of the proportion of subjects with HbA_{1c} <7.0% (and HbA_{1c} <6.5% and HbA_{1c} <7.5%) due to few subjects meeting the threshold. In this case, a logistic regression model will be used. The model will include treatment and stratification factor as fixed effects, and baseline HbA_{1c} value as a covariate. This alternative approach will be applied on the LOCF data at Week 26/Week 52 and the observed data by visit. Odds ratios and the 2-sided 95% CIs for the treatment comparisons will be derived from the model.

The time to event data (e.g., time to receiving rescue therapy or discontinuing due to need for rescue therapy) will be plotted using the KM method. The difference in proportion of subjects receiving rescue therapy or discontinuing due to need for rescue therapy between canagliflozin and placebo with 95% confidence intervals will be provided.

22

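### Do the weighted dose-versus-placebo HbA1c comparisons in SAP 5.4.2 need a stated model, placebo weight, missing-data rule and variance?

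*SAP*

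**What the plan says.** SAP 5.4.2 states that the two comparisons by dose "will be tested for reference purpose by using the weights in the analyses described below". For HbA1c, what follows is a weighting rule and nothing else. Everyone starts at 1. After Week 12, in the comparison for 100 mg without increase, canagliflozin subjects "re-randomized to continue canagliflozin 100 mg will have a weight of 2. The subjects who are re-randomized to up-titrate to canagliflozin 300 mg" get 0. In the comparison for 100 mg increased to 300 mg, the 2 and the 0 change places. Protocol 11.3.2 gives the same rule and also names no model.

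The surrounding text is as follows:

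- SAP 1.5: eligible subjects "will be re-randomized in a 1:1 ratio (in a blinded fashion via IWRS) to either" stay on their assignment or up-titrate. On placebo: "In order to keep the study blind, subjects randomized to the placebo group will undergo a mock up-titration".
- SAP 5.4.1 defines both dose endpoints as change in HbA1c at Week 26.
- SAP 5.2.3: the primary analysis of that variable is multiple imputation followed by a Week 26 ANCOVA. On the imputation: "An MI regression will be applied to impute all monotone missing values, using treatment group, stratification factors, baseline HbA1c and the change from baseline" at Weeks 6, 12 and 20.
- SAP 5.3.2, for the endpoints of Section 5.3: "Continuous endpoints (except for triglycerides) will be analyzed with an MMRM model as described before in the FAS population".
- SAP 5.4.2 does name methods for its other variables: ANCOVA with LOCF for lipids, rank methods for triglycerides, and for blood pressure "The change from baseline in SBP and DBP will be analyzed using an MMRM model".
- The SAP Amendment 3 log records the demotion of the repeated-measures model: "Furthermore, since MMRM is not the primary efficacy analysis, the following sentence has been deleted".

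**The concern.** The dose comparisons serve two additional secondary objectives (SAP 1.1), yet the programmer is given weights without an analysis to put them in. HbA1c has several analyses in SAP 5.2.3, and none is linked to the weights. Two features make the gap look more than cosmetic.

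First, a weight that starts at 1 and changes after Week 12 sounds like a weight attached to visits. It would then act differently from a single weight only in a repeated-measures model, and that combination can bias the estimate. Second, subjects weighted 2 stand in for others, so the number of independent observations is smaller than the sum of the weights. A careless variance would make the intervals too narrow. Eligible placebo subjects also pass through a mock re-randomization, so one might ask whether they too should be weighted 2 and 0.

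**Working it through.** **Inputs.** From SAP 1.4: effects 0.5 (not re-randomized), 0.4 (stay on 100 mg) and 0.5 (up-titrated), SD 0.9, 50% re-randomized, 66 evaluable and 73 randomized per arm. From SAP 1.5: re-randomization 1:1.

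**1. The plan's own figure.** The pooled effect is 0.5 × 0.5 + 0.25 × 0.4 + 0.25 × 0.5 = 0.475. With 66 per group, SE = 0.9 × √(2/66) = 0.1567, and the noncentral t distribution gives 85.3% power. Then 66 × 1.10 = 72.6, rounded up to 73. The stated sample size reproduces. The plan states no power for the dose comparisons.

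**2. Are the weights right?** A re-randomized subject has probability 1/2 of each path, so the inverse-probability weight is 2 for the path of interest and 0 for the other. With 73 canagliflozin subjects, the expected numbers are 36.5 at weight 1, 18.25 at 2 and 18.25 at 0, and the weights sum to 36.5 + 36.5 = 73. The targets are

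- 100 mg: (36.5 × 0.5 + 36.5 × 0.4)/73 = 0.45
- 100 to 300 mg: (36.5 × 0.5 + 36.5 × 0.5)/73 = 0.50

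These are the effects wanted. The weights are valid.

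**3. The placebo weight.** All subjects start at 1, and the only changes listed are for subjects re-randomized to canagliflozin 100 mg or 300 mg. Mock-titrated placebo subjects fall in neither class and stay at 1.

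**4. The model.** The endpoint is defined at Week 26 only. It is the primary variable, whose current analysis is the Week 26 ANCOVA on imputed data. The repeated-measures rule in SAP 5.3.2 covers the Section 5.3 endpoints, where HbA1c change appears at Weeks 12 and 52 but not at Week 26 by dose. In a Week 26 analysis, the change after Week 12 simply fixes each subject's final weight.

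**5. Standard error** (73 per arm, no dropout, no covariates). Effective canagliflozin n = (Σw)²/Σw² = 73²/(36.5 + 4 × 18.25) = 5329/109.5 = 48.7.

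- True SE, placebo at 1: 0.9 × √(1/48.7 + 1/73) = 0.167.
- Weights used as model precision weights: residual variance inflated by 146/(36.5 + 18.25 + 73 − 2) = 1.161, so SE = 0.149 × √1.161 = 0.161. A nominal 5% test then has a true error of about 5.9%.
- Weights used as frequencies: 0.9 × √(2/73) = 0.149, with a true error of about 8.0%.
- Placebo also weighted 2 and 0: 0.9 × √(2/48.7) = 0.182.

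For a re-randomized share of 30 to 80% (assumed range), the precision-weight error is 5.6 to 6.2% and the frequency-weight error 6.8 to 9.8%.

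**6. Week 26 weighted ANCOVA by simulation.** There were 5,000 trials per setting, 73 per arm, about 10% missing at random, and 20 imputations from treatment, baseline and Week 12 change. Assumed: 50 or 65% re-randomized and Week 12 to 26 correlation 0.3 to 0.8. Bias was at most 0.007. Model SE over true SE was 0.96 to 0.985, with coverage 94.0 to 94.7% (Monte Carlo error about 0.3 points). A sandwich variance gave 95.1 to 95.6%, with intervals about 4% wider (0.690 against 0.663 at 50% and correlation 0.5).

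**7. The adverse coding.** Put the weights on visits in a repeated-measures model, drop the Week 26 records of weight-0 subjects and keep their earlier ones. The model fills in the dropped values from Week 12, while the retained Week 12 non-responders are also doubled. They count twice and the effect shrinks. At 50% re-randomized and an assumed baseline SD of 1.2, the shift toward zero is:

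| Correlation | 100 mg | 100 to 300 mg |
|---|---|---|
| 0.3 | 0.021 | 0.020 |
| 0.5 | 0.036 | 0.034 |
| 0.8 | 0.070 | 0.061 |

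Over all settings tried (baseline SD 0.6 to 1.5), the shift is 0.018 to 0.098 (4 to 22%) for 100 mg and 0.016 to 0.086 (3 to 17%) for 100 to 300 mg. At correlation 0.5 in the table it is about 0.2 SE.

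**The case for a change.** The case for amending is respectable. The section names a method for every other variable it covers and none for HbA1c by dose. The words about starting at 1 and changing after Week 12 do fit a repeated-measures model, and a programmer who applied them by visit could shrink both estimates. The comparisons are to be tested, so the standard error matters, and frequency coding would turn a 5% test into an 8% one. Three or four sentences would close all of this without new data.

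What stands is that the model, the missing-data method and the variance are not written down. The rest carries less weight. The shrinkage needs a chain of choices that the SAP nowhere makes: a repeated-measures model, weights by visit, and weight-0 subjects kept at early visits only. Treating analysis weights as frequencies is an error that a competent analyst avoids. The placebo weight is settled by the text. Prescribing a sandwich variance would move coverage from about 94.0–94.7% to 95.1–95.6%, for a comparison with no stated power.

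**Conclusion.** No change to the plan is needed. The weights are valid, placebo stays at 1, and the natural analysis is the Week 26 ANCOVA on the primary analysis's imputed data with one final weight per subject. Under it the consequences are a bias of at most 0.007 HbA1c points and a model-based standard error 2 to 4% too small. Both are negligible for comparisons labelled as reference and kept outside the testing sequence in SAP 5.1.1 and Protocol 11.3.2. This is missing detail that analysts fill sensibly.

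The conclusion rests on that Week 26 reading. The bias and coverage figures also rest on a simplified imputation: it had no separate pattern for intercurrent events, no stratification terms and 20 rather than 1000 imputations. They therefore indicate size and do not validate the exact SAP procedure. The SAP's imputation model has one canagliflozin group, so imputed values pool the two doses; the simulation pooled them too, and at 10% missing that effect is within the 0.007. The conclusion would differ only if the programming applied weights by visit inside a repeated-measures model, which the documents do not call for.

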Bayesian Analysis of the Primary Efficacy Endpoint for overall study and subset of subjects with metformin (with or without insulin) will be performed in the event that the study on its own yields non-significant result based on primary efficacy analysis. Full details of the Bayesian analysis will be included in a separate supplemental SAP.

Sensitivity and supportive Analyses

The following sensitivity analyses will also be performed, all aligned with the primary estimand:

- A Copy Reference MI model will be performed (Ratitch 2013). After any intermediate missing data will be imputed based on MCMC, monotone missing data will be imputed as following:
 - For the canagliflozin group, imputation will be performed using an imputation model based on the placebo/reference group, conditional on the stratification factors, baseline HbA_{1c} and the observed change from baseline values at previous time points relative to the mean of the model for the placebo group. Participants in the canagliflozin group will be imputed as if they had always been members of the placebo group.
 - For the placebo group, imputation will assume Missing at Random.
 - A total of 1000 multiple imputations will be performed. A seed equal to 345 will be used in all MI models.
 - After MI, each of the multiple imputed datasets will be analyzed using ANCOVA with terms for treatment, stratification factors, and baseline HbA_{1c}.
 - Rubin's rules will be applied to combine the ANCOVA results across the imputed datasets.
- A tipping point analysis will also be performed. This analysis starts with a MAR MI model (intermediate missing imputed with MCMC and monotone missing imputed with a MI regression model, using treatment group, stratification factors, baseline HbA_{1c} and the change from baseline in HbA_{1c} at Weeks 6, 12 and 20). Then each imputed value for monotone missing in the canagliflozin group will be made worse by a difference Delta. Each imputed dataset will be analyzed using ANCOVA and Rubin's rules will be applied to combine the ANCOVA results across the imputed datasets. A sequence of Delta worsening adjustments will be applied, starting with zero with increments of 0.1 until the results reach statistical non-significance. The results corresponding to all applied Delta adjustments will be plotted together with the results from the primary analysis, Copy Reference MI analysis and the other sensitivity analyses.

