- The primary efficacy endpoint will be analyzed using a mixed model for repeated measures (MMRM) based on restricted maximum likelihood. The analysis will use the observed data and will include the fixed, categorical effects of treatment, stratification factors (ie, background AHA and age group), visit, and treatment-by-visit interaction, as well as the fixed,

continuous covariates of baseline and baseline-by-visit interaction. An unstructured covariance will be used to model the within-patient errors. In case the model does not converge using the unstructured covariance then alternative covariance structures (such as compound symmetry and AR(1)) will be considered.

• The change from baseline in HbA_{1c} will be analyzed using an ANCOVA model with treatment and the stratification factors as fixed effects and baseline HbA_{1c} value as a covariate. The treatment differences in the least-squares means and the 2-sided 95% CI will be estimated based on this model. The last observation carried forward (LOCF) method will be applied when the Week 26 values are missing.

In addition, based on the FAS with the data collected up to Week 26, the following supportive analysis will be performed:

- A re-randomization test (Proschan 2011) (utilizing the MMRM) will be used to determine the p-value for the treatment comparison of the primary efficacy endpoint (ie, comparing all subjects who are randomized to canagliflozin to all subjects who are randomized to placebo). The re-randomization test will fix the observed HbA_{1c} data, regenerate treatment assignments for the entire study using the same minimization algorithm employed in the study and compute the test statistics corresponding to the treatment comparison. This process will be repeated at least 1,000 times. The p-value for the treatment comparison will be defined as the proportion of re-randomized studies whose test statistic for that comparison is at least as extreme as that of the original treatment assignment.
- A supportive analysis of the primary endpoint will be conducted based on the 26-week PP analysis set using the same mixed model with repeated measures as in the sensitivity analysis.

Subgroup Analyses

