5.3. Secondary Efficacy Endpoints

5.3.1. Definition

The secondary efficacy endpoints at Week 26 and Week 52 include:

- Change from baseline in FPG.
- The proportion of subjects with $HbA_{1c} < 7.5\%$, <7.0%, and <6.5%.
- Time to rescue and proportion of subjects receiving rescue therapy.

- Percent change from baseline in body weight.
- Change from baseline in BMI.
- Percent change from baseline Fasting plasma lipids (ie, LDL-C, HDL-C, total cholesterol, non-HDL-C, LDL-C to HDL-C ratio, non-HDL-C to LDL-C ratio, and triglycerides).
- Change from baseline in SBP and DBP.

The secondary efficacy endpoint at Week 12 and Week 52:

• Change from baseline in HbA_{1c}.

The analysis of the above endpoints will use the same attributes of the primary estimand except that the population level summary for the categorical endpoints will be difference in proportions.

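### SAP 5.3.2 and 5.4.2 give fasting lipids two unreconciled analysis rules, and the one that deals with missing values uses LOCF

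*SAP*

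**What the plan says.** SAP 5.3.1 includes "Percent change from baseline Fasting plasma lipids" among the secondary endpoints at Weeks 26 and 52. SAP 5.4.1 lists percent change in lipids again, at the same two weeks, as another efficacy variable.

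The methods differ:

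- **SAP 5.3.2.** "For the endpoints with post-baseline assessments taken only at Week 26 and Week 52", the plan is that "an analysis of covariance (ANCOVA) model similar to the primary efficacy endpoint will be used at Week 26". Missing values are not mentioned. Lipids fall under this rule, because 5.4.2 itself notes: "Given that lipids are only collected at baseline, Week 26 and Week 52". Protocol 11.3.3 gives the same rule.
- **SAP 5.4.2.** Lipids other than triglycerides are analysed by ANCOVA at Week 26 and at Week 52, "with LOCF applied when the Week 26 or Week 52 values are missing". It adds: "The model will be similar to the supportive approach listed in Section 5.2.3".

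SAP 5.2.3 also has an LOCF ANCOVA of HbA1c: "The last observation carried forward (LOCF) method will be applied when the Week 26 values are missing". It stands in a list introduced by: "The following sensitivity analyses will also be performed, all aligned with the primary estimand". Protocol 11.3.1 likewise places it under the primary estimand. That estimand (SAP 5.2.2) uses a treatment-policy strategy for treatment discontinuation and for rescue, and 5.3.2 applies it to the secondary endpoints with only the variable changed.

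**The concern.** An endpoint with two permitted analyses can give two answers, and nothing in the SAP fixes beforehand which is reported as the lipid result. The choice could then be made after unblinding.

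The only rule that deals with missing lipid values is also a weak one. LOCF assumes that a subject's lipids stayed where they were last measured, which may be just after the last dose, six months earlier at Week 26, or before treatment began. It then enters that value as if it had been observed, so the standard error carries no allowance for having filled it in. LDL-C is where this matters most: Protocol 1.1.3 reports a rise with canagliflozin in adults and calls LDL-C an established cardiovascular risk factor.

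**Working it through.** The point turns on no figure in the plan, so there is none to reproduce. The check has three parts.

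**1. The two rules side by side**

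| | SAP 5.3.2 | SAP 5.4.2 |
|---|---|---|
| Scope | Any endpoint sampled after baseline only at Weeks 26 and 52 | Lipids by name |
| ANCOVA at | Week 26 | Weeks 26 and 52 |
| Model referred to | Primary endpoint | Supportive approach in 5.2.3 |
| Missing values | Not named | LOCF |
| Triglycerides | Nonparametric or another method, left open | Wilcoxon rank sum with Hodges-Lehmann |

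The reference from 5.4.2 to 5.2.3 does not resolve. The analyses that 5.2.3 now calls supportive are a re-randomization test and a per-protocol MMRM. The ANCOVA with LOCF stands among the sensitivity analyses.

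**2. What LOCF would carry.** The Time and Events Schedule takes lipids on Day 1, at Week 26, and at Week 52, end of treatment or early withdrawal.

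- Missing Week 26: the last value is an early-withdrawal sample, due as soon as possible after the last dose, or else baseline.
- Missing Week 52: the last value is an early-withdrawal sample or the Week 26 sample, or else baseline.

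The SAP does not say whether baseline may be carried.

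**3. Size and direction.** Let Δ be the canagliflozin-minus-placebo difference in subjects who have the effect, and m the share with a missing value, taken as equal in both arms.

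(a) The Week 26 value is carried to Week 52, the effect is the same at both visits in subjects still treated, and it is fully lost in those with missing values:
- target = (1 − m)Δ; LOCF gives Δ; error = +mΔ.

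(b) Baseline is carried, so the change is zero in both arms, while the subjects concerned in truth keep the effect (for example, still on drug but with no sample):
- target = Δ; LOCF gives (1 − m)Δ; error = −mΔ.

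The two bounds need opposite assumptions about the missing subjects. If baseline is carried and the effect was in fact lost, the difference is not biased by this route.

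Inputs: m = 0.10, borrowed from the attrition inflation in SAP 1.4, which is not a forecast of missing lipid values; adult LDL-C differences of 4.4 mg/dL (100 mg) and 8.2 mg/dL (300 mg) from Protocol 1.1.3. The SAP endpoint is percent change, so the mg/dL figures only give scale.

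- (a) Overstatement: 0.10 × 4.4 = 0.44 mg/dL; 0.10 × 8.2 = 0.82 mg/dL.
- (b) Estimated difference: 0.90 × 4.4 = 3.96 mg/dL; 0.90 × 8.2 = 7.38 mg/dL.
- (b) over m = 5% to 30%: 4.18 down to 3.08 mg/dL, and 7.79 down to 5.74 mg/dL.

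For the HbA1c LOCF analysis, the average planned effect from SAP 1.4 is 0.5 × 0.5 + 0.25 × 0.4 + 0.25 × 0.5 = 0.475 points. Under the assumptions of (a), the overstatement is 0.475m: 0.024, 0.048 and 0.095 points at 5%, 10% and 20% missing.

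**The case against.** The best defence is that 5.3.2 states a general model and 5.4.2 the specific lipid rule, which adds Week 52, a missing-data method and a definite triglyceride test. On that reading, similarity to the primary endpoint means only the ANCOVA terms. The primary imputation model in 5.2.3 uses HbA1c at Weeks 6, 12 and 20, when lipids are not sampled, so it could not be copied to lipids as written. This is a fair reading, and it stands that 5.3.2 never mentions imputation. But the SAP does not say that 5.4.2 takes precedence, and that reading leaves LOCF as the governing method.

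Three stronger conclusions might be inferred, and the documents do not support them.

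- *That LOCF abandons treatment policy.* It acts only where the Week 26 or Week 52 value is missing. Protocol 10.2.4 keeps subjects who stop drug on scheduled visits with laboratory assessments, and values obtained there are used. LOCF is therefore a missing-data assumption under an unchanged intercurrent-event strategy, and in that sense the heading in 5.2.3 can be defended.
- *That LOCF always preserves a drug effect.* The working shows that the direction depends on which value is carried and on what happened to the subject.
- *That blood pressure has the same conflict.* It is also listed twice, but 5.3.2 and 5.4.2 both lead to an MMRM, so the duplicate is harmless.

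The safety reading of LDL-C also has another source: SAP 6 and 6.2 summarise laboratory tests, including lipids, without imputation.

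**Conclusion.** The concern holds as a minor one. Lipids have two rules that differ on missing data, time points and reference model, and the cross-reference to 5.2.3 is out of date. LOCF is at fault for its missing-data assumption and for ignoring imputation uncertainty. How far the intervals would be too narrow cannot be computed from the documents.

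With 10% missing, the bias is at most about 10% of the effect in either direction, or 0.44 to 0.82 mg/dL on the adult LDL-C figures. The upper bound assumes full washout in subjects whose Week 26 value is carried to Week 52. The lower bound assumes that baseline is carried for subjects who keep the effect. The primary test does not use LOCF, and SAP 5.1.1 keeps the secondary endpoints out of the testing sequence, so only the interpretation of supportive results is affected.

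**What to change.** - State one lipid rule for Weeks 26 and 52 in one section: ANCOVA after multiple imputation, combined by Rubin's rules. Imputation predictors would be treatment, stratification factors, baseline lipid and, for Week 52, the Week 26 value.
- Do not simply delete the 5.4 lipid text. It holds the only explicit Week 52 lipid ANCOVA and the only definite triglyceride method. Move both into the single rule, keep Wilcoxon and Hodges-Lehmann for triglycerides, and remove the open wording in 5.3.2.
- Correct the reference from 5.4.2 to 5.2.3.
- Keep any LOCF result, including the HbA1c ANCOVA, only as a supplementary analysis, with its missing-data assumption written out and a statement of whether baseline may be carried.
- The duplicate blood pressure entry can be dropped for tidiness.

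The cost is SAP wording and a small amount of extra programming. No data collection or sample size changes.
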